8.1.2 Technical Computation Details for Primary Efficacy Analysis

The SAS code for the PROC MIXED procedure to carry out the above MMRM analysis with an unstructured variance covariance structure is illustrated as follows:

```
proc mixed;
  class treatment center visit subjid;
  model change=treatment center visit treatment*visit baseline*visit / s cl
  ddfm=kenwardroger;
  repeated visit /type=un subject=subjid r rcorr;
```

SAP 405-201-00013

```
lsmeans treatment*visit / pdiff cl alpha=0.05 slice=visit;
run;
```

where baseline is the last AISRS Total score prior to the first dose of double-blind IMP in the double-blind treatment period.

8.1.3 Sensitivity Analyses

8.1.3.1 Sensitivity Analyses for Missing at Random (MAR) Assumption

Traditionally the dropout mechanisms are divided into three types (Little, 1995): (1) Missing Completely at Random (MCAR), in which the probability of dropout doesn't depend on the observed data and the missing data; (2) Missing at Random (MAR), in which the probability of dropout depends on the observed data, and (3) Missing Not at Random (MNAR), where the probability of dropout depends on the missing data and possibly the observed data.

Most of MNAR methods (Diggle P, Kenward MG, 1994) have treated all observations with dropout as if they fall within the same dropout type. In practice, we would find that different dropout reasons may be related to the outcomes in different ways, for example, detailed dropout reasons for this study are: adverse events (AE), lack of efficacy (LOE), lost to follow-up, protocol deviation, sponsor discontinued study, subject met (protocol specified) withdrawal criteria, subject was withdrawn from participation by the investigator, and subject withdrew consent to participate. Dropout due to an AE and LOE may lead to MNAR dropout. Subject withdrew consent may also lead to MNAR dropout. However, it is debatable whether a dropout caused by subjects withdrew consent is MAR or MNAR. Except AE, LOE, and subject withdrew consent, all the other dropout reasons may be assumed as either MCAR or MAR dropout. Dropout due to COVID-19 will also be assumed as MAR.

As sensitivity analyses for missing at random (MAR) assumption, analyses for missing not at random (MNAR) will be carried out. Pattern Mixture Models (PMM) based on Multiple Imputation (MI) with mixed missing data mechanisms will be used to investigate the response profile of dropout patients by last dropout reason under MNAR mechanism for the following three scenarios:

- 1) Dropout reasons due to either AE or LOE as MNAR
- 2) Dropout reasons due to either AE or LOE or subject withdrew consent as MNAR
- 3) All dropouts as MNAR

Delta Adjustment Imputation Methods

This MNAR sensitivity analysis is to departure from MAR assumption by progressively increasing the delta until conclusion from the primary analysis is overturned. The delta is 0%, 10%, 20%, 30%, ..., 100% of the expected treatment difference of 5 points and/or the observed

SAP 405-201-00013

treatment difference between centanafadine and Placebo from the primary analysis of MMRM model until conclusion of the primary analysis is overturned. When $\delta=0$ it is MAR. When $\delta > 0$ it is MNAR.

- 1) Using Monte Carlo Markov Chain (MCMC) methodology from PROC MI to impute the intermittent missing data to a monotone missing pattern;
- 2) Using a standard MAR-based multiple imputation approach from PROC MI to impute the monotone missingness data
- 3) For patients in the treated group and with a dropout reason of AE or LOE or subject withdrew consent, a delta will be added for all the values after the dropout time.
- 4) Using MMRM model in the primary analysis to analyze the completed data using PROC MIXED on the multiple imputed data
- 5) Obtaining the overall results using PROC MIANALYZE.

Placebo Based Imputation Methods

Similar to “Standard” multiple imputations, except parameters for imputation model obtained from only the placebo (control) group. Missing data for both placebo and drug group are imputed based on the imputation model derived from placebo data. If drug improved outcomes prior to dropout, this benefit is carried into subsequent imputed values, but will diminish over time in accordance with the correlation structure.

In addition, model based MNAR methods such as the shared parameter model (Wu and Bailly, 1989) and random coefficient pattern mixture model (Hedeker D, Gibbons RD, 1997) will be also performed.

LOCF and OC Analyses

Change from baseline of the double-blind treatment period for the AISRS total score will be evaluated using ANCOVA with baseline of the double-blind treatment period value as covariate and treatment and, in LOCF analyses, study center as main effects. For the OC analyses, study center will not be included in the model.

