3.8.3.2 Documenting Reasons for Treatment Discontinuation

A subject may discontinue IMP for a number of reasons including those listed below:

- Reasons related to AE:
 - Subject decides to discontinue because of annoyance or discomfort due to a non-serious AE which is not otherwise determined to be an undue hazard
 - Continuing IMP places the subject at undue risk as determined by the investigator (eg, a safety concern that is possibly, probably, or likely related to IMP)
 - SAE
- Death
- Reasons unrelated to medical condition (provide detail and review AE history with subject)
- Withdrawal of informed consent (complete written withdrawal of consent form)
- Lost to follow-up
- Rash (regardless of severity or seriousness) (see [Section 5.4](#))
- Pregnancy (see [Section 5.7](#))
- Termination of all or part of the trial by the sponsor
- Lack of efficacy (LOE)

Subjects withdrawn prior to Day 42 must complete the Day 42/ET evaluations at the time of withdrawal. In addition, all subjects who withdraw prematurely from the trial will be assessed by telephone 1, 3, and 5 days after the last dose of IMP, in the clinic 2 and 7 days after the last dose of the IMP, and 10 days via telephone after the last dose of the IMP. Three attempts will be made to contact the subject by telephone; in the event the site is unable to reach the subject by telephone, the site will attempt to contact the subject via certified mail or an alternative similar method where appropriate.

Meeting a screening exclusion criterion post-randomization does not require an automatic discontinuation of the subject. The investigator should assess the change for clinical significance, determine if an AE should be reported, and make a determination of subject continuation based on subject safety. The investigator will consult with the medical monitor to determine subject continuation in the trial.

If the subject discontinues IMP due to an AE, the investigator, or other trial personnel, will make every effort to follow the event until it has resolved or stabilized. Follow-up procedures in [Section 5.9](#) must be followed.

Protocol 405-201-00013

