7.1 Sample Size

The primary efficacy endpoint is the change from baseline at Day 42 in AISRS total score. The trial will compare the placebo arm to the centanafadine dose arms, randomized at a ratio of 1:1:1, with an overall alpha of 0.05 for the primary endpoint.

Based on the results at various dose strengths from phase 2 centanafadine trials, it is reasonable to expect a treatment difference of 5 points with a standard deviation (SD) of 12.5 in the mean change from baseline to Day 42 on AISRS total score in either the 200 mg TDD or 400 mg TDD arms. The planned sample size of 405 evaluable subjects (135 in each treatment arm) will yield at least 90% power to detect the treatment effects at a 2-tailed significance level of 0.05. The 2-sided alpha level for the final analysis is 0.05.

A sufficient number of subjects will be enrolled and randomized to achieve approximately 405 evaluable subjects in the double-blind treatment period (ie, subjects with an AISRS total score at baseline and at least 1 subsequent AISRS total score in the

Protocol 405-201-00013

double-blind treatment period). After allowance of 10% nonevaluable subjects in the double-blind treatment period, the total number of subjects to be randomized is 450 subjects (150 subjects in each treatment arm). In order to ensure 405 evaluable subjects, the number of nonevaluable subjects will be monitored in a blinded manner on an ongoing basis during the trial. The power and sample size were obtained using the PASS 14 (2015) statistical computing software.

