7.3.1.1 Sensitivity Analyses

7.3.1.1.1 Sensitivity Analyses for Missing at Random Assumption

Traditionally the dropout mechanisms are divided into 3 types⁴³: (1) missing completely at random (MCAR), in which the probability of dropout doesn't depend on the observed data and the missing data; (2) MAR, in which the probability of dropout depends on the observed data, and (3) MNAR, where the probability of dropout depends on the missing data and possibly the observed data.

Most of MNAR methods⁴¹ have treated all observations with dropout as if they fall within the same dropout type. In practice, we would find that different dropout reasons may be related to the outcomes in different ways, for example, detailed dropout reasons for this trial are: AE, LOE, death, reasons unrelated to medical condition, withdrawal of informed consent, lost to follow-up, rash, pregnancy, and termination of all or part of the trial by sponsor. Dropout due to an AE, rash, and LOE may lead to MNAR dropout. Subjects that withdrew consent may also lead to MNAR dropout. However, it is debatable whether a dropout caused by subjects that withdrew consent are MAR or MNAR. Except AE, rash, LOE, and subjects that withdrew consent, all the other dropout reasons may be assumed as either MCAR or MAR dropout.

As sensitivity analyses for MAR assumptions, analyses for MNAR will be carried out. Pattern Mixture Models based on MI with mixed missing data mechanisms will be used

Protocol 405-201-00013

to investigate the response profile of dropout subjects by last dropout reason under the MNAR mechanism for the following 3 scenarios:

- 1) Dropout reasons due to either AE, rash, or LOE as MNAR
- 2) Dropout reasons due to either AE, rash, or LOE or subject withdrew consent as MNAR
- 3) All dropouts as MNAR

Delta Adjustment Imputation Methods

This MNAR sensitivity analysis will be performed to address a departure from the MAR assumptions by progressively increasing the delta until the conclusion from the primary analysis is overturned. The delta is 0%, 10%, 20%, 30%, .., 100% of the expected treatment difference of 5 points and/or the observed treatment difference between centanafadine and placebo from the primary analysis of MMRM model until the conclusion of the primary analysis is overturned. When delta=0 it is MAR. When delta > 0 it is MNAR.

- 1) Using Monte Carlo Markov Chain methodology from PROC MI to impute the intermittent missing data to a monotone missing pattern;

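### Rash is an MNAR dropout reason in protocol 7.3.1.1.1 but not in the SAP, and delta step 3 does not follow the scenarios, so rash withdrawals coded outside AE may escape the delta shift

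*SAP*

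**What the plan says.** Protocol 3.8.3.2 gives rash its own entry among the reasons for stopping IMP, separate from the AE-related ones: "Rash (regardless of severity or seriousness". Protocol 7.3.1.1.1 keeps that separation. It names rash with AE and LOE as possibly leading to MNAR dropout, and its first scenario reads "Dropout reasons due to either AE, rash, or LOE as MNAR". Scenario 2 adds withdrawal of consent, and scenario 3 takes all dropouts.

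SAP 8.1.3.1 follows the same text closely but uses a different reason list without rash. Its scenario 1 is AE or LOE, scenario 2 adds withdrawal of consent, and scenario 3 is all dropouts. On the remaining reasons it says "Except AE, LOE, and subject withdrew consent, all the other dropout reasons may be assumed as either MCAR or MAR dropout". Those remaining reasons include "subject met (protocol specified) withdrawal criteria" and withdrawal by the investigator.

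Delta step 3, in both documents, adds delta to treated-group dropouts whose reason is AE, LOE or withdrawn consent. It says nothing about which scenario is being run.

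**The concern.** Newly acquired, non-traumatic skin eruption is the adverse event of special interest in this program, and the protocol deliberately put rash among the reasons for which MAR is least secure. The SAP removes it without explanation.

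The delta analysis asks how far MAR must fail among active-arm dropouts before the conclusion is overturned. Delta is added only in the treated group, and a positive delta worsens the AISRS. Leaving out an active-arm dropout who belongs in the MNAR set therefore leaves the estimate unchanged or keeps it further from placebo, and it can raise the delta at which the result tips. What is at stake is how stringent these sensitivity analyses are, not the primary test.

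**Working it through.** **1. The passages side by side**

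| Place | Scenario 1 | Scenario 2 | Scenario 3 |
|---|---|---|---|
| Protocol 7.3.1.1.1 | AE, rash, LOE | plus withdrew consent | all dropouts |
| Protocol 7.2 | AE, LOE | plus withdrew consent | all dropouts |
| SAP 5.2 | AE, LOE | plus withdrew consent | all dropouts |
| SAP 8.1.3.1 | AE, LOE | plus withdrew consent | all dropouts |
| Delta step 3, both documents | AE, LOE, withdrew consent | same | same |

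Two mismatches follow. Rash appears in one row of five. Step 3 matches only the SAP's scenario 2: read literally, it shifts too many subjects in scenario 1 (consent withdrawals) and too few in scenario 3.

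**2. What happens to one active-arm rash withdrawal under the SAP**

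- Coded AE: it receives delta in all three scenarios.
- Coded as meeting withdrawal criteria, or as withdrawn by the investigator: no delta in scenarios 1 and 2. In scenario 3 it receives delta under the scenario's title but not under step 3.
- Placebo-based imputation: covered whatever the code.
- Primary MMRM: all dropout is handled under MAR, so the code is irrelevant.

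**3. The plan's own figures**

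This point has no stated figure of its own. The 5-point delta comes from protocol 7.1: "it is reasonable to expect a treatment difference of 5 points with a standard deviation (SD) of 12.5". That calculation reproduces. SE = 12.5 × √(2/135) = 1.521; 5/1.521 = 3.286; power = Φ(3.286 − 1.960) = 0.908 (0.906 with the noncentral t), against "The planned sample size of 405 evaluable subjects (135 in each treatment arm) will yield at least 90% power". Also 405/0.90 = 450. The fix changes none of these.

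**4. Illustration of size**

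Inputs are from the output appended to the SAP. For 400 mg versus placebo at Day 42 (STAT-4.1.1) the estimate is −2.7448, SE 1.3267, df 392, p = 0.0392, upper 95% limit −0.1364. The arm has 147 subjects (STAT-4.2), of whom 119 are observed at Day 42 (STAT-4.7), so 147 − 119 = 28 have no Day 42 value.

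Moving k dropouts from MAR to MAR plus delta shifts the arm mean by k × delta/147. With delta = 5, that is 0.034 per subject. Holding SE and df fixed and shifting no other dropout:

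| k | Estimate | p |
|---|---|---|
| 0 | −2.745 | 0.039 |
| 1 | −2.711 | 0.042 |
| 2 | −2.677 | 0.044 |
| 3 | −2.643 | 0.047 |
| 4 | −2.609 | 0.050 |
| 5 | −2.575 | 0.053 |
| 10 | −2.405 | 0.071 |

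The number needed to reach p = 0.05 is 0.1364 × 147/5 = 4.0 at delta = 5, and 0.1364 × 147/2.7448 = 7.3 when delta equals the observed difference. For 200 mg (upper limit −0.5139, also 147 subjects) it is 0.5139 × 147/5 = 15.1.

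This is not a rerun of the multiple imputation. In a real run the AE and LOE dropouts are shifted as well. The actual k is not in the documents.

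**The case against.** The strongest reply is that rash is an adverse event. Protocol 3.5.4 describes it as one of special interest, and SAP 9.1 treats it within adverse events. On the SAP's condensed list, AE is its natural home, and AE is MNAR. The SAP list also lacks the protocol's separate entries for death and pregnancy, so rash was not singled out. This has force: many or all rash withdrawals may have been coded AE. It does not settle the matter. Safety classification does not fix the disposition category, the protocol separates the two reasons twice, and no passage says how a rash withdrawal is coded.

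A second reply is that other analyses cover the gap. Placebo-based imputation does. So, by intent, does scenario 3: SAP section 13 plans separate delta tables for each of the three scenarios. That suggests scenario-specific runs were meant, but the wording of step 3 does not deliver them.

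A reader might go further and infer that scenarios 1 and 2 are biased in favor of centanafadine. The documents do not support that. The effect depends on unseen coding, the SAP says only that other reasons may be assumed MCAR or MAR, and its estimand in 8.1.1 is the effect had nobody withdrawn, so a placebo-level outcome after stopping is not the target. A reader might also take a rash withdrawal rate from phase 2, where five of eight subjects with rash stopped dosing. Protocol 1.3 states that neither subject with rash at 400 mg did so. None of those who stopped was therefore on 400 mg, and no rate for this trial follows.

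**Conclusion.** The point holds as a contradiction between protocol and SAP, together with a delta rule that does not match its own scenarios. The protocol is also inconsistent with itself: its section 7.2 and its delta step 3 omit rash, while 7.3.1.1.1 includes it.

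The consequence is conditional. If every rash withdrawal was coded AE, nothing changes. If some were coded elsewhere, the delta analyses in scenarios 1 and 2, and in scenario 3 on a literal reading, may be less stringent for centanafadine. The size cannot be stated because the number of such subjects is not given. The illustration shows only that for 400 mg a handful could matter (about 4 at a 5-point delta), while 200 mg would need about 15, both with the standard error fixed and no other dropout shifted. The primary MMRM, the placebo-based imputation, the sample size, power and alpha are unaffected.

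**What to change.** 1. In SAP 5.2 and 8.1.3.1, count any withdrawal for skin eruption as MNAR in scenarios 1 and 2, as protocol 7.3.1.1.1 does. Identify it from the AE/AESI record with IMP withdrawn, whatever disposition category was ticked.
2. Reword delta step 3 so that delta goes to treated-group dropouts whose reason is MNAR under the scenario being run: scenario 1, AE, rash or LOE; scenario 2, those plus withdrawn consent; scenario 3, all dropouts.
3. Align protocol 7.2 and protocol delta step 3 with this.

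The cost is wording and one derived flag from data already collected. Adding rash can only leave the delta-adjusted estimate unchanged or move it toward placebo, so the sensitivity results may be slightly less favorable. The step 3 rewording also removes consent withdrawals from scenario 1, where the literal text would now shift them. If the flag finds no rash withdrawal coded outside the reasons already shifted, adding rash changes no result, and one sentence can say so.

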5.2 Handling of Missing Data

The mixed-effect model repeated measure (MMRM) assumes data are missing at random (MAR), which is a reasonable assumption in longitudinal clinical trials in MDD¹. However, the possibility of “missing not at random” (MNAR) data can never be ruled out. As sensitivity analyses, selection model², pattern-mixture model^{3,4,5,6}, and/or shared parameter model⁷ will be used to explore data missing mechanisms of MNAR and investigate the response profile of dropout patients by last dropout reason under MNAR mechanism for the following 3 scenarios: 1) Dropout reasons due to either AE or LOE as MNAR, 2) Dropout reasons due to either AE or LOE or subject withdrew consent as MNAR, 3) All dropouts as MNAR using

SAP 405-201-00013

both 1) Delta adjustment imputation method which is to departure from MAR assumption by progressively increasing the delta until conclusion from the primary analysis is overturned, and 2) Placebo based imputation methods in which missing data for both placebo and drug group are imputed based on the imputation model derived from placebo data. If drug improved outcomes prior to dropout, this benefit is carried into subsequent imputed values, but will diminish over time in accordance with the correlation structure. Details are provided in [Section 8.1.3](#) Sensitivity Analysis.

The observed-cases (OC) data set will consist of actual observations recorded at each visit during the double-blind treatment period and no missing data will be imputed. MMRM, Wu-Bailey, and pattern-mixture model will be performed on the OC dataset.

The last-observation-carried-forward (LOCF) data set will include data recorded at a scheduled double-blind treatment period visit or, if no observation is recorded at that visit, data carried forward from the previous scheduled double-blind treatment period visit. Baseline data (e.g., the last visit of the single-blind placebo run-in period) will not be carried forward to impute missing values for the LOCF data set. The analysis of covariance (ANCOVA) analysis will be performed for the change from baseline to the end of the double-blind treatment period (Day 42, LOCF) in AISRS total score as sensitivity analysis. The ANCOVA_LOCF model includes treatment and study center as main effects, and baseline value as a covariate.

ANCOVA analysis with OC data will also be conducted on change from baseline for AISRS total score, as well as all continuous change from baseline efficacy endpoints.

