- CT-5.9.4 Summary of Mean Change from Baseline to End of Single-Blind Placebo Run-in Period in ASRS Inattentive Subscale - OC (Efficacy Sample)
- CT-5.9.5 Summary of Mean Change from Baseline of the Double-Blind Treatment Period to the Double-Blind Treatment Period by Study Day in ASRS Hyperactive-Impulsive Subscale - MMRM, UN (Efficacy Sample)
- CT-5.9.6 Summary of Mean Change Baseline of the Double-Blind Treatment Period to the Double-Blind Treatment Period by Study Day in ASRS Hyperactive-Impulsive Subscale - LOCF (Efficacy Sample)
- CT-5.9.7 Summary of Mean Change from Baseline of the Double-Blind Treatment Period to the Double-Blind Treatment Period by Study Day in ASRS Hyperactive-Impulsive Subscale - OC (Efficacy Sample)
- CT-5.9.8 Summary of Mean Change from Baseline to End of Single-Blind Placebo Run-in Period in ASRS Hyperactive-Impulsive Subscale - OC (Efficacy Sample)
- CT-5.10.1 Summary of Mean Change from Baseline of the Double-Blind Treatment Period to the Double-Blind Treatment Period by Study Day in Adult ADHD Investigator Symptom Rating Scale (AISRS) Total Score – MI, VAN ELTEREN TEST (Efficacy Sample)
- CT-5.10.2 Summary of Mean Change from Baseline of the Double-Blind Treatment Period to the Double-Blind Treatment Period by Study Day in Adult ADHD Investigator Symptom Rating Scale (AISRS) Total Score - GEE (Efficacy Sample)
- CT-5.10.3 Summary of Mean Change from Baseline of the Double-Blind Treatment Period to the Double-Blind Treatment Period by Study Day in Adult ADHD Investigator Symptom Rating Scale (AISRS) Total Score - WGEE (Efficacy Sample)
- CT-5.11.1 Sensitivity Analysis of MNAR using Pattern Mixture Model with Multiple Imputation (Delta Method 1) in AISRS Total Score Assume All Dropouts as MNAR (Efficacy Sample)

SAP 405-201-00013

- CT-5.11.2 Sensitivity Analysis of MNAR using Pattern Mixture Model with Multiple Imputation (Delta Method 2) in AISRS Total Score Assume All Dropouts as MNAR (Efficacy Sample)
- CT-5.11.3 Sensitivity Analysis of MNAR using Pattern Mixture Model with Multiple Imputation (Delta Method 1) in AISRS Total Score Dropout due to AE or LOE or Withdrew Consent as MNAR (Efficacy Sample)
- CT-5.11.4 Sensitivity Analysis of MNAR using Pattern Mixture Model with Multiple Imputation (Delta Method 2) in AISRS Total Score Dropout due to AE or LOE or Withdrew Consent as MNAR (Efficacy Sample)

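### Step 3 of the delta-adjustment algorithm is worded for scenario 2 only; applied as written, the delta tables for all three MNAR scenarios would be the same analysis

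*SAP*

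**What the plan says.** SAP 8.1.3.1 defines three scenarios. Scenario 1 is "Dropout reasons due to either AE or LOE as MNAR". Scenario 2 widens the set: "Dropout reasons due to either AE or LOE or subject withdrew consent as MNAR". Scenario 3 is "All dropouts as MNAR". SAP 5.2 ties the same three to the delta method, in which delta is raised step by step until the primary conclusion no longer holds, and also to placebo-based imputation. Section 13 gives each scenario its own pair of delta tables for the AISRS total score: CT-5.11.1 and 5.11.2 (for example "Delta Method 1) in AISRS Total Score Assume All Dropouts as MNAR"), CT-5.11.3 and 5.11.4 for scenario 2, and CT-5.11.5 and 5.11.6 for scenario 1. CT-5.11.8 to 5.11.13 are the CGI-S counterparts, although the title of CT-5.11.12 names a different scale.

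SAP 8.1.3.1 then gives a single five-step algorithm. Step 3 covers subjects in the treated group "with a dropout reason of AE or LOE or subject withdrew consent, a delta will be added"; the shift applies to every later value. Protocol 7.3.1.1.1 has the same step. Neither document says that the set changes with the scenario.

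**The concern.** A scenario is defined by which dropouts are allowed to depart from MAR, and step 3 is the only place where that choice enters the computation. If step 3 always names the same reasons, the scenario label on a table does not alter the numbers in it. The all-dropouts tables matter most here. They are the widest of the three delta scenarios, and a reader will take their tipping point as allowing for every treated-arm dropout. If dropouts for other reasons stay at MAR, fewer subjects carry the penalty, a larger delta is needed to overturn the conclusion, and the result looks sturdier than it is.

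**Working it through.** **Comparing the sets.** The SAP's dropout reasons outside step 3 are "lost to follow-up, protocol deviation, sponsor discontinued study, subject met (protocol specified) withdrawal criteria, subject was withdrawn from participation by the investigator", and it separately holds COVID-19 dropout at MAR.

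| Delta tables (AISRS) | Set that should be shifted | Set that step 3 shifts | Consequence |
|---|---|---|---|
| CT-5.11.5, 5.11.6 (scenario 1) | AE, LOE | AE, LOE, consent withdrawal | Too many shifted if any treated subject withdrew consent; robustness understated |
| CT-5.11.3, 5.11.4 (scenario 2) | AE, LOE, consent withdrawal | The same | Correct |
| CT-5.11.1, 5.11.2 (scenario 3) | All dropouts | AE, LOE, consent withdrawal | Too few shifted if any treated dropout has another reason; robustness overstated |

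Protocol 7.3.1.1.1 has a further mismatch. Its scenarios 1 and 2 include rash as a reason separate from AE, but its step 3 does not mention rash, so there step 3 matches none of the three scenarios exactly. Protocol 7.2 and the SAP state the scenarios without rash.

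**Plan figure.** The delta grid is built on the expected 5-point difference, which is also the design effect. With SD 12.5 and 135 per arm, the standard error is 12.5 × √(2/135) = 1.52, and power is Φ(5/1.52 − 1.96) = 0.908. This agrees with the stated minimum of 90%, and nothing here changes it.

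**Illustrating the size.** The inputs are from the outputs appended to the SAP:
- Day 42 differences from the primary model (STAT-4.1.1): 400 mg −2.7448 (SE 1.3267, df 392); 200 mg −3.1497 (SE 1.3407, df 400).
- Efficacy Sample (STAT-4.2): 147 per active arm. Observed at Day 42 (STAT-4.7): 119 on 400 mg and 109 on 200 mg.
- Share missing, m: 400 mg 28/147 = 0.1905; 200 mg 38/147 = 0.2585.

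Let q be the fraction of those missing subjects who receive delta. The arm mean worsens by about delta × m × q. With the standard error held fixed, significance is lost at

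tipping delta = (|difference| − t × SE) / (m × q).

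Numerators, with t = 1.966:
- 400 mg: 2.7448 − 1.966 × 1.3267 = 0.1365
- 200 mg: 3.1497 − 1.966 × 1.3407 = 0.5139

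These agree, to rounding, with the printed upper confidence limits of −0.1364 and −0.5139.

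| q | 400 mg tipping delta | 200 mg tipping delta |
|---|---|---|
| 1 (true scenario 3) | 0.72 | 1.99 |
| 0.75 | 0.96 | 2.65 |
| 0.50 | 1.43 | 3.98 |
| 0.25 | 2.87 | 7.95 |

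The 5-point grid moves in steps of 0.5. With all missing subjects shifted, the conclusion is first overturned at 1.0 point (400 mg) and 2.0 points (200 mg). With half shifted, this happens at 1.5 and 4.0. With a quarter shifted, 200 mg is never overturned within the grid.

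**The case against.** The strongest reply is that the intended analyses are clear. The scenario list and the table titles separate the three cases, and a literal step 3 would produce three identical pairs of tables, which a programmer would notice. On this view step 3 is a worked example for scenario 2. That is a fair account of the likely intent, and it means that wrong tables are a risk and not an established outcome. But neither document says that step 3 is an example. The same SAP section also says that reasons other than AE, LOE and consent withdrawal may be taken as MCAR or MAR, and that COVID-19 dropout is MAR, with no exception for scenario 3. Two careful programmers could therefore produce different all-dropouts tables, each defensible from the text.

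A reader might infer more: that the trial's robustness has been overstated throughout, or that no check on all missing data remains. The documents do not support either. The scenario 1 error is conservative. Placebo-based imputation (CT-5.11.7) is not restricted by dropout reason and does not use step 3, and the shared-parameter and random-coefficient pattern-mixture models are also untouched. No delta-adjusted result appears in the material available, so it cannot be said which set was shifted in practice.

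The limits on the size also stand. Reasons by arm are not given, so every q below 1 is an assumption. A missing Day 42 value may be an intermittent gap, or an assessment excluded for falling more than three days after the last dose. Multiple imputation would give its own standard error. The 400 mg comparison, which is tested first, tips early on the grid both when all and when half of its missing subjects are shifted.

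**Conclusion.** The point holds as a wording error in a stated rule. Step 3 describes scenario 2, and followed literally it gives the wrong analysis for scenarios 1 and 3, in opposite directions. The set comparison needs no numerical assumption; whether a table actually changes depends on there being treated-arm dropouts in the categories concerned. The effect is confined to the delta-method tables for AISRS and CGI-S. The primary analysis, the testing order, the sample size and the other sensitivity analyses are unaffected. The tipping deltas show what could be at stake and do not measure an error that occurred: they rest on a fixed standard error, on missing at Day 42 as a proxy for dropout, and on outputs run in June 2020, after the SAP was approved in April 2020. The correction should be made, but it does not call the primary result into question.

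**What to change.** Reword step 3 in SAP 8.1.3.1 and Protocol 7.3.1.1.1 along these lines: *For subjects in the treated groups whose dropout reason is in the MNAR set of the scenario being run, delta is added to all values after dropout.*

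In the same edit:
- State whether COVID-19 dropouts stay at MAR or are shifted in scenario 3. Without this, the new wording would conflict with the SAP sentence that holds them at MAR.
- Align rash across Protocol 7.2, the scenarios and step 3 of Protocol 7.3.1.1.1, and the SAP, saying whether it is counted within AE or as a separate reason.

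If the tables have already been produced, confirm and record which set each one shifted.

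The cost is a few sentences and one programming parameter. Relative to tables built from step 3 as written, scenario 3 tipping points become smaller (less favourable) and scenario 1 tipping points become larger; scenario 2 is unchanged apart from whatever is decided on rash.
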